## **Appendix 2. Requirement for prohibited concomitant medications in the therapeutic anticoagulation (experimental arm)**

### **Dual therapy with any of the following:**

Aspirin  
Clopidogrel  
Ticagrelor  
Prasugrel

### **Single agent therapy with any of the following:**

Dabigatran  
Rivaroxaban  
Apixaban  
Edoxaban  
Melagatran  
Inogatran  
Argatroban  
Bivalirudin  
Lepirudin  
Desirudin  
Hirudin  
Alteplase  
Streptokinase  
Urokinase  
Reteplase  
Tenecteplase

## Appendix 3. Fraction of Inspired Oxygen (FiO2) for Various Oxygen Delivery Devices

For all supplemental oxygen delivery devices, the patient is not just breathing the direct oxygen, but rather is breathing a **combination** of room air plus the oxygen from the supplemental device. Different devices deliver to the patient more or less of a % of what is coming in from the tank.

0 (no oxygen, just room air)	21%
------------------------------	-----

### For a Nasal Cannula:

[figure not shown]
Oxygen tank FLOW RATE in liters / min	FiO2 -- Fraction of Inspired Oxygen value
1 L / min	24%
2 L / min	28%
3 L / min	32%
4 L / min	36%
5 L / min	40%
6 L / min	44%

### For a Simple Face Mask – Low Flow (approximate values):

Oxygen tank FLOW RATE in liters / min	FiO2 -- Fraction of Inspired Oxygen value
5 L / min	35%
6 L / min	39%
7 L / min	43%
8 L/min	47%
9 L/min	51%
10 L/min	55%

**For a Venturi Mask (approximate values):**

The FiO2 is controlled by both the L/min as well as by the valve as indicated by its colour (see below). Note colours may vary based on institution (please double check locally). See example below, the colour of the valve is the best indicator of the FiO2 provided.

**Nonrebreather (approximate value):**

Oxygen tank FLOW RATE in liters / min	FiO 2 -- Fraction of Inspired Oxygen value
15 L/min	90%

**High Flow Nasal Cannula:**

**For the purposes of this trial, a patient is considered to be receiving high flow nasal cannula (HFNC) therapy when the flow rates provided by this device are >30 L/min.**

For HFNC therapy, the FiO2 and flow rate are independent settings.

Thus, you cannot infer the FiO2 based on the flow rate.

The user controls both and thus should simply enter the FiO2 that was set for the patient.

## Appendix 4. Outcome Definition for Organ-support Free Days

### Outcome Definition for Organ-support Free Days

Defined as the number of days that a patient is alive and free of organ support through 28 days after trial entry. Organ support is defined as receipt of non-invasive mechanical ventilation, high flow nasal cannula oxygen, invasive mechanical ventilation, or vasopressor therapy.

- Non-invasive mechanical ventilation is defined as BIPAP or CPAP when used for acute respiratory support (the use of BIPAP or CPAP at night or when sleeping for sleep apnea is not considered organ support).
- High Flow Nasal Cannula Oxygen is defined as receiving  $\geq 30$  l/min flow at  $\text{FiO}_2 \geq 40\%$ .
- Invasive mechanical ventilation is defined as positive pressure ventilation through endotracheal tube or tracheostomy.
- Vasopressor support includes infusion of any vasoactive or inotropic medication.
- A patient must be extubated and not receiving mechanical ventilation for at least 2 days before being considered free of mechanical ventilation. If a patient was extubated and re-intubated and placed back on mechanical ventilation within 1 or 2 days, the patient is considered to be on mechanical ventilation during those 1 or 2 days before re-intubation.
- Any patient dying in the acute hospital stay are assigned 28 Day Organ-Support Free Days of -1.
- If there is intervening time in which a patient is free of organ support but goes back on organ support the intervening time does not count toward the organ support free days endpoint. Only time before organ support and after the last use of organ support are counted as "free days."
- If a patient was discharged alive without mechanical ventilation prior to Day 28, the patient is assumed to be free of organ support after hospital discharge for the remainder of the 28 days.
- If a patient was discharged alive on mechanical ventilation (invasive or non-invasive) prior to day 28, a call to the patient or a doctor/nurse from the rehabilitation health facility is needed to confirm ventilation status on day 28 and their last day of mechanical ventilation.

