### ***6.3 Endpoint Assessment***

**Primary outcome (primary endpoint):** The primary composite outcome of ICU admission, non-invasive positive pressure ventilation, invasive mechanical ventilation or death at 28 days.

If a patient is discharged alive before 28 days, vital status will be determined using a telephone follow-up. If a patient was discharged alive on mechanical ventilation (invasive or non-invasive) prior to day 28, a call to the patient or a doctor/nurse from the rehabilitation health facility is needed to confirm ventilation status on day 28 and their last day of mechanical ventilation.

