4.3 Secondary Outcomes Analysis

For the secondary outcomes outlined in section 2.2.1, a chi-squared test of independence will be used to compare the proportions between groups where appropriate. Odds ratios with 95% confidence intervals, and p values will be reported.

Hospital-free days alive, ICU-free days alive, ventilator-free days and organ support-free days will be respectively analyzed as: the number of days out of hospital alive; the number of days out of ICU alive; the number of ventilator-free days alive (alive and free of invasive mechanical ventilation); and the number of organ support-free days alive (alive and free of invasive mechanical ventilation, non-invasive mechanical ventilation, high flow nasal cannula oxygen and vasopressor therapy) through day 28;

death up to 28 days will be assigned a value of -1. These outcomes will be analyzed using ordinal logistic regression.

The post-treatment D-dimer will be compared by means of linear regression (ANCOVA), adjusted for baseline. Since the D-dimer assay differed across sites, the raw values are not comparable. Therefore, the D-dimer will be analyzed as the logarithm of D-dimer x upper limit of normal (ULN) by taking the natural logarithm of the ratio of the actual d-dimer value divided by the ULN for the assay used.

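### Appendix 4's post-discharge rule for organ support-free days tests mechanical ventilation only, yet credits freedom from all four organ supports

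*Protocol*

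**What the plan says.** Protocol Appendix 4 defines the components: "Organ support is defined as receipt of non-invasive mechanical ventilation, high flow nasal cannula oxygen, invasive mechanical ventilation, or vasopressor therapy". Free days are those before the first and after the last use of support. When a patient comes off support and later returns to it, "the intervening time does not count toward the organ support free days endpoint".

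For time after discharge there are two bullets. The first reads "If a patient was discharged alive without mechanical ventilation prior to Day 28, the patient is assumed to be free of organ support after" discharge, up to day 28. The second covers the others: "If a patient was discharged alive on mechanical ventilation (invasive or non-invasive) prior to day 28, a call to the patient" or to a clinician at the rehabilitation facility is required, to learn ventilation status on day 28 and the last ventilated day. The general follow-up in Protocol 6.3 is narrower: "If a patient is discharged alive before 28 days, vital status will be determined using a telephone follow-up". Table 5 lists organ support at each data entry to day 28, taken from the chart when available, and its footnote says the entries span all 28 days.

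SAP 4.3 analyses days "alive and free of invasive mechanical ventilation, non-invasive mechanical ventilation, high flow nasal cannula oxygen and vasopressor therapy" through day 28 by ordinal logistic regression and gives -1 for death up to 28 days. It does not repeat the discharge assumption. Appendix 4 gives -1 only for death in the acute hospital stay.

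For the primary outcome, SAP 3.2.1 has a comparable assumption. It covers only patients who lack a 28-day assessment and were event-free when discharged alive.

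**The concern.** The condition for the assumption is narrower than what the assumption grants. Being off a ventilator at discharge is taken to mean being off all four supports from discharge to day 28. Two kinds of patient are exposed.

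- **Discharged on high-flow oxygen or a vasopressor.** The bullet applies to them as worded, so support that is known to be running on the day they leave is scored as absent from then on.
- **Discharged off support, then readmitted and supported before day 28.** The discharge bullet says free, while the intervening-time bullet says that free time before a return to support is not counted.

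Both kinds can receive days they did not have. The trial is open-label, so discharge or transfer practice could differ by arm. If it did, the excess credit would not cancel. If it did not, the excess would mainly add noise.

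**Working it through.** The plan states no figure for this rule, so there is none to reproduce. The check sets the bullets side by side and then scores example patients.

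**1. Trigger against credit (Appendix 4).** The second discharge bullet specifies both forms of ventilation, so the supports left out are the other two.

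| Support at discharge | Counts as organ support | Assumed free afterwards | Call asks for its last day |
|---|---|---|---|
| Invasive ventilation | yes | no | yes |
| Non-invasive ventilation | yes | no | yes |
| High-flow nasal oxygen | yes | yes | no |
| Vasopressor | yes | yes | no |

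**2. Scoring.** For a survivor, Appendix 4 gives

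free days = (first support day - 1) + (28 - last support day), or 28 if there is no support.

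The definition uses all support days to day 28. The discharge bullet, read literally, uses only support up to discharge. All dates below are assumed, because the documents give none.

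| Patient | By the definition | By the discharge bullet | Excess |
|---|---|---|---|
| High-flow oxygen days 2-16, leaves day 8 | 1 + 12 = 13 | 1 + 20 = 21 | 8 |
| High-flow oxygen days 8-28, leaves day 10 | 7 + 0 = 7 | 7 + 18 = 25 | 18 |
| No support, home day 6, readmitted, intubated days 10-20 | 9 + 8 = 17 | 28 | 11 |
| High-flow oxygen days 5-8, home day 10, readmitted, ventilated days 15-22 | 4 + 6 = 10 | 4 + 20 = 24 | 14 |

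The first two rows are the high-flow or vasopressor case, where the text is clear. The last two are the readmission case, where the second column follows the intervening-time bullet and the third follows the discharge bullet.

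**3. Coherence.** SAP 4.3 counts ventilator-free days as days alive and free of invasive ventilation. The third patient has 28 - 11 = 17. Organ support includes invasive ventilation, so organ support-free days should not exceed 17. The discharge bullet read literally gives 28.

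**4. Scale in an arm.** The number of such patients is not in the documents. Assume 0.5% to 5% of an arm of 231:

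- 231 x 0.005 = 1.2 patients, and 231 x 0.05 = 11.6 patients.
- With 8 to 18 excess days each, the arm mean rises by 0.005 x 8 = 0.04 to 0.05 x 18 = 0.9 days.

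The planned analysis is ordinal and does not compare means, so this range shows scale only.

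**The case against.** **Assumed may simply mean filling in what was not observed.** On that reading, support recorded at readmission is counted under the intervening-time bullet, and Table 5 provides for collecting it to day 28 when the chart is available. This stands in part. A reader might infer that the plan definitely scores a recorded readmission as support-free. The documents do not settle that; they contain two bullets that disagree and no order of precedence.

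**The SAP may not differ.** A reader might infer from SAP 4.3's silence that the two documents score these patients differently. That is not shown. SAP section 1 says it is to be read together with the protocol, so silence may import the Appendix 4 rule. The death score is a separate matter, and there the two texts do differ.

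**Leaving on these supports may be rare.** Neither document says whether transfer to another acute hospital is a discharge, and the call rule mentions a rehabilitation facility. If transfer is not discharge, few patients would leave on high-flow oxygen or a vasopressor (a judgement, not a documented figure). This limits the size but does not remove the gap. The appendix itself provides for patients leaving while ventilated, and exclusion criterion 14 allows high-flow oxygen at entry.

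**An odds ratio would overstate the effect.** Suppose any-support risks of 35% and 25%. The odds ratio for no support is (0.75/0.25)/(0.65/0.35) = 1.62. Hiding 10% of supported patients in the lower-risk arm only gives (0.775/0.225)/(0.65/0.35) = 1.85; hiding 10% in both gives (0.775/0.225)/(0.685/0.315) = 1.58. The 1.85 is not evidence of impact. It rests on an assumed one-arm rate and a dichotomy that is not the planned analysis. It also does not measure the high-flow and vasopressor case, because those patients already count as supported.

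**Conclusion.** The discharge bullet misfires as written for patients who leave alive on high-flow oxygen or a vasopressor: they are credited with freedom from support that is known to be running, and no call corrects it. For readmission with recorded support, the finding is an unresolved conflict between two bullets of the same list. Unlike SAP 3.2.1, the bullet is not limited to missing assessments or to patients free of the event at discharge.

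The excess is 8 to 18 days per affected patient in the examples, on assumed dates. The number affected is unknown and probably small. Direction is also unknown: similar excess in both arms mostly adds noise, while a difference between arms in discharge or transfer could bias the result either way.

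It would be too broad to say that everyone discharged alive is scored free to day 28. Patients discharged on ventilation are followed up, and under SAP 4.3 any death by day 28 scores -1. One secondary outcome is affected. Protocol 7.2 calls the secondary outcomes exploratory, and the primary outcome has its own rule and is untouched. The change is still worth making, because otherwise analysts must choose between readings once data exist.

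**What to change.** Reword the Appendix 4 bullet and repeat it in SAP 4.3, for example: *A patient discharged alive on none of the four organ supports is assumed free of organ support thereafter, unless organ support before day 28 is recorded (for example at readmission or after transfer), in which case the recorded support days are used.*

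In addition:

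- State whether transfer to another acute hospital counts as discharge.
- Widen the call for patients discharged on ventilation to those discharged on any organ support as defined, asking for the last day of that support.
- Align the -1 rule, which is death in the acute hospital stay in Appendix 4 and death up to 28 days in SAP 4.3.

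The cost is a few sentences of text and one extra question in a telephone follow-up that is already planned for patients discharged alive. Only outcome scoring changes.

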1. INTRODUCTION

This statistical analysis plan (SAP) outlines the planned statistical methods for the summary and analysis of data collected within the scope of the Coagulopathy of COVID-19 (RAPID COVID COAG) trial protocol version 1.4 dated October 13, 2020.

The SAP should be read in conjunction with the study protocol and the electronic Case Report Form (eCRF). This version of the SAP has been developed using the final version of the protocol mentioned above and eCRF version 1.3 dated September 17, 2020.

All statistical analyses will be performed using R version 3.6.2 and/or Stata version 15.1, or higher.

2. STUDY OBJECTIVES

2.1 Primary Objective

To determine the effect of therapeutic anticoagulation, with low molecular weight heparin (LMWH) or high dose nomogram of unfractionated heparin (UFH) compared to standard care in hospitalized patients admitted for coronavirus disease 2019 (COVID-19) with an elevated D-dimer on the composite outcome of intensive care unit (ICU) admission, non-invasive mechanical ventilation (positive pressure ventilation), invasive mechanical ventilation or death at 28 days.

Primary Outcome

The primary outcome of this trial is the difference in proportions of subjects with the composite of ICU admission, non-invasive or invasive mechanical ventilation or death between groups within the first 28 days post-randomization.

2.2 Secondary Objectives

To compare the following secondary outcomes between the experimental group receiving therapeutic doses of LMWH or high dose nomogram of UFH and the control group receiving standard care:

2.2.1 Secondary Outcomes

- 1) Proportion of all-cause death within the first 28 days post-randomization.
- 2) Proportion of subjects with the composite outcome of ICU admission or all-cause death within the first 28 days post-randomization.
- 3) Proportion of subjects with the composite outcome of invasive or non-invasive mechanical ventilation or all-cause death within the first 28 days post-randomization.

- 4) Proportion of subjects with major bleeding, as defined by the ISTH Scientific and Standardization Committee (ISTH-SSC), within the first 28 days post-randomization.
- 5) Proportion of subjects with red blood cell transfusion ≥ 1 unit within the first 28 days post-randomization.
- 6) Proportion of subjects who experienced the following: transfusion of platelets, frozen plasma, prothrombin complex concentrate, cryoprecipitate and/or fibrinogen concentrate within the first 28 days post-randomization.
- 7) Proportion of subjects who had renal replacement therapy defined as continuous renal replacement therapy (CRRT) or intermittent hemodialysis (IHD) within the first 28 days post-randomization.
- 8) Hospital-free days alive up to day 28 post-randomization.
- 9) ICU-free days alive up to day 28 post-randomization.
- 10) Ventilator-free days alive up to day 28 post-randomization.
- 11) Organ support-free days alive up to day 28 post-randomization.
- 12) Proportion of subjects who had venous thromboembolism defined as symptomatic or incidental, suspected or confirmed via diagnostic imaging and/or electrocardiogram where appropriate, recognizing that access to diagnostic imaging may be limited in the midst of the COVID-19 pandemic. Confirmatory testing at a later date once exposure risk/personal protective utilization is not an issue is encouraged within the first 28 days post-randomization.
- 13) Proportion of subjects who had arterial thromboembolism defined as suspected or confirmed via diagnostic imaging and/or electrocardiogram where appropriate, recognizing that access to diagnostic imaging may be limited in the midst of the COVID-19 pandemic. Confirmatory testing at a later date once exposure risk/personal protective utilization is not an issue is encouraged within the first 28 days post-randomization.
- 14) Proportion of subjects with heparin induced thrombocytopenia within the first 28 days post-randomization.
- 15) D-dimer, a COVID-19 disease-related biomarker at day 2 $+$ /- 24 hours post-randomization.

In addition, the following pre-specified components of the primary composite outcome will be analyzed (not pre-specified in the protocol):

- 16) Proportion of subjects with ICU admission.
- 17) Proportion of subjects with the composite of invasive or non-invasive mechanical ventilation.
- 18) Proportion of subjects with invasive mechanical ventilation.

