## 4.0 Study Population

The study population includes hospitalized adults admitted for COVID-19 prior to the development of critical illness. We have excluded individuals where the bleeding risk or risk of transfusion would generally be considered unacceptable, those already therapeutically anticoagulated and those who would have already met components of our primary outcome. Participants are recruited from hospital sites in Argentina, Brazil, Canada, Ireland, Saudi Arabia, United Arab Emirates, and the United States of America.

The inclusion criteria are:

- 1) Laboratory confirmed COVID-19 (diagnosis of SARS-CoV-2 via reverse transcriptase polymerase chain reaction as per the World Health Organization protocol or by nucleic acid based isothermal amplification). Positive test prior to hospital admission **OR** within first 5 days (i.e. 120 hours) after hospital admission;
- 2) Admitted to hospital for COVID-19;
- 3) One D-dimer value above ULN (within 5 days (i.e. 120 hours) of hospital admission) **AND EITHER:**
  - a. D-Dimer  $\geq$ 2 times ULN **OR**
  - b. D-Dimer above ULN and Oxygen saturation  $\leq$  93% on room air;
- 4)  $\geq$  18 years of age;
- 5) Informed consent from the patient (or legally authorized substitute decision maker).

The exclusion criteria are:

- 1) pregnancy;
- 2) hemoglobin  $<80$  g/L in the last 72 hours;
- 3) platelet count  $<50 \times 10^9$ /L in the last 72 hours;
- 4) known fibrinogen  $<1.5$  g/L (if testing deemed clinically indicated by the treating physician prior to the initiation of anticoagulation);
- 5) known INR  $>1.8$  (if testing deemed clinically indicated by the treating physician prior to the initiation of anticoagulation);
- 6) patient already on intermediate dosing of LMWH that cannot be changed (determination of what constitutes an intermediate dose is to be at the discretion of the treating clinician taking the local institutional thromboprophylaxis protocol for high risk patients into consideration);
- 7) patient already on therapeutic anticoagulation at the time of screening (low or high dose nomogram UFH, LMWH, warfarin, direct oral anticoagulant (any dose of dabigatran, apixaban, rivaroxaban, edoxaban);
- 8) patient on dual antiplatelet therapy, when one of the agents cannot be stopped safely;
- 9) known bleeding within the last 30 days requiring emergency room presentation or hospitalization;
- 10) known history of a bleeding disorder of an inherited or active acquired bleeding disorder;

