**Table 1. Therapeutic Dose Anticoagulation**

Any of the following strategies may be used for high-dose anticoagulation:

CrCl	BMI	Enoxaparin	Dalteparin	Tinzaparin	UFH	
$\geq 30$	<40	1 mg/kg SC q12h OR 1.5 SC mg/kg q24h	200 units/kg SC q24h OR 100 IU/kg SC q12h	175 U/kg SC q24h	IV bolus, with continuous infusion to titrate to institution specific anti-Xa or aPTT values*	
	$\geq 40$	1 mg/kg q12h &	100 units/kg SC q12h &	175 U/kg SC daily &		
$<30$	<40	UFH IV bolus, with continuous infusion to titrate to institution specific anti-Xa or aPTT values* or LMWH per hospital protocol taking BMI into consideration as above				
	$\geq 40$					

Abbreviations: CrCl = creatinine clearance; BMI = body mass index; \* Initial bolus dose determined by sites, encouraging use of dosing algorithm designed for treatment of VTE. UFH anti-Xa titration is preferred over aPTT if available as achieving a therapeutic aPTT may be challenging in patients with a pro-inflammatory state such as COVID-19.

&For patients with BMI above 40, measurement of anti-Xa to confirm therapeutic effect can be used.

Table 2 outlines the investigational products chosen for this study, mechanism of action and rationale for use.

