**Prophylactic Dose Anticoagulation**

CrCl	BMI	Enoxaparin	Dalteparin	Tinzaparin	Fondaparinux	Unfractionated Heparin (UFH)
$\geq 30$	<40	40 mg SC q24h	5000 units SC q24h	4500 U SC q24h	2.5 mg SC q24h	5000 units SC q8-12h
	$\geq 40$	40 mg SC q12h	5000 units SC q12h	9000 (+/- 1000) U SC q24h	not applicable	7500 units SC q8h
<30	<40	UFH 5000 units SC q8-12h or LMWH per hospital protocol taking BMI into consideration as above				
	$\geq 40$	UFH 7500 units SC q8h or LMWH per hospital protocol taking BMI into consideration as above				

Abbreviations: CrCl = creatinine clearance; BMI = body mass index

Type and doses of thromboprophylactic LMWH or UFH will be recorded in the case report forms. Concomitant medications and co-enrollment of other COVID-19 trials will also be recorded.

Full therapeutic dose anticoagulation (therapeutic dose UFH or LMWH) is permitted as rescue therapy in the event of suspected or confirmed thromboembolism. Additional rescue therapy, in the form of thrombolysis (with tissue plasminogen activator), is also permitted if deemed clinically warranted by the treating clinical team.

Institutional drug stock will be used, and the institutional pharmacy will be responsible for labelling and distribution. No repackaging of drugs will occur.

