**Secondary outcomes (secondary endpoints), evaluated up to day 28, include:**

- 1) All-cause death;
- 2) Composite of ICU admission or all-cause death;
- 3) Composite of mechanical ventilation or all-cause death;
- 4) Major bleeding as defined by the ISTH Scientific and Standardization Committee (ISTH-SSC) recommendation (21);
- 5) Red blood cell transfusion ( $\geq 1$  unit);
- 6) Transfusion of platelets, frozen plasma, prothrombin complex concentrate, cryoprecipitate and/or fibrinogen concentrate;
- 7) Renal replacement therapy defined as continuous renal replacement therapy {CRRT} or intermittent hemodialysis {IHD};
- 8) Hospital-free days alive;
- 9) ICU-free days alive;
- 10) Ventilator-free days alive;

- 11) Organ support-free days alive (see Appendix 4 for definition);
- 12) Venous thromboembolism (defined as symptomatic or incidental, suspected or confirmed via diagnostic imaging and/or electrocardiogram where appropriate recognizing that access to diagnostic imaging may be limited in the midst of the COVID-19 pandemic, however confirmatory testing at a later date once exposure risk/personal protective utilization is not an issue is encouraged);
- 13) Arterial thromboembolism (defined as suspected or confirmed via diagnostic imaging and/or electrocardiogram where appropriate recognizing that access to diagnostic imaging may be limited in the midst of the COVID-19 pandemic, however confirmatory testing at a later date once exposure risk/personal protective utilization is not an issue is encouraged);
- 14) Heparin induced thrombocytopenia;
- 15) Trajectories of COVID-19 disease-related biomarkers.

Outcome measures will be obtained from participants' hospital medical records and where applicable through a telephone follow-up, as outlined in Table 5: Study Schedule of Events. The use of BIPAP or CPAP at night or when sleeping for sleep apnea is not considered non-invasive mechanical ventilation or organ support for the purpose of this trial.

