∞to be obtained from hospital medical record or verbally from patient if not available from medical record and patient is aware of their blood group;

†Phlebotomy and sample processing on day 1, 3, and 14 OR the time of discharge OR reaching a component of primary outcome OR study withdrawal for any reason;

§Research staff will enter data into REDCap on screening, randomization (day 1), Days 3, 7, 14, and 28 including data from the days in between. Data entered will cover the entire 28 day period. Day 3 will cover Day 2 to Day 3, Day 7 will cover Day 4 to Day 7, Day 14 will cover Day 8 to Day 14, and Day 28 will cover Day 15 to Day 28. If multiple laboratory results are available, the most pathological value since last assessment will be recorded;

within 5 days (i.e. 120 hours) of hospital admission;

screening and randomization can be done on the same day;

 For participants treated with UFH: aPTT or UFH anti-Xa will be drawn according to local institutional UFH nomogram protocol guidance;

If patient is discharged alive before 28 days, vital status will be determined using telephone follow-up by a research coordinator; the use of BIPAP or CPAP at night or when sleeping for sleep apnea is not considered non-invasive mechanical ventilation or organ support for the purpose of this trial; If a patient was discharged alive on mechanical ventilation (invasive or non-invasive) prior to day 28, a call to the patient or a doctor/nurse from the rehabilitation health facility is needed to confirm ventilation status on day 28 and their last day of mechanical ventilation.

Bleeding defined as by ISTH Scientific and Standardization Committee (ISTH-SSC) recommendation: 1) Fatal bleeding, and/or 2) symptomatic bleeding in critical area or organ (such as intracranial, intraspinal, intraocular, retroperitoneal, intraarticular or pericardial, or intramuscular with compartment syndrome, and/or 3) bleeding causing a fall of hemoglobin level of 20g/L or more, or leading to transfusion of two or more units of whole blood or red cells;

6aDefined as  $\geq 1$  unit;

6bDefined as platelet, frozen plasma, prothrombin complex concentrate, cryoprecipitate, fibrinogen concentrate;

defined as continuous renal replacement therapy or intermittent hemodialysis;

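### Secondary outcome 7 counts any hemodialysis within 28 days and maintenance-hemodialysis patients are not excluded, so recorded pre-existing dialysis is scored as an event in either arm and dilutes the odds ratio

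*SAP*

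**What the plan says.** The outcome has the same content wherever it is defined. SAP 2.2.1, item 7: "Proportion of subjects who had renal replacement therapy defined as continuous renal replacement therapy (CRRT) or intermittent hemodialysis (IHD", counted over the 28 days after randomization. Protocol 6.3, secondary outcome 7: "Renal replacement therapy defined as continuous renal replacement therapy {CRRT} or intermittent hemodialysis {IHD". Footnote 7 to Table 5 describes the data item as "defined as continuous renal replacement therapy or intermittent hemodialysis". None of these asks for new onset or sets aside patients already on dialysis.

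On eligibility, Protocol 4.0 summarises its exclusions this way: "We have excluded individuals where the bleeding risk or risk of transfusion would generally be considered unacceptable, those already therapeutically anticoagulated", and adds patients who already met a component of the primary outcome. The 16 listed criteria contain no dialysis, end-stage renal disease or creatinine criterion. Both dosing tables have rows for creatinine clearance below 30 with no lower limit. Table 1 (experimental arm) reads "UFH IV bolus, with continuous infusion to titrate to institution specific anti-Xa or aPTT values* or LMWH per hospital protocol"; Table 3 (control arm, BMI below 40) reads "UFH 5000 units SC q8-12h or LMWH per hospital protocol taking BMI into consideration as above".

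SAP 4.3 analyses the binary secondary outcomes with a chi-squared test and an odds ratio. SAP 4.4 to 4.6 (subgroups, sensitivity analyses, missing data) do not mention baseline dialysis.

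**The concern.** A patient on maintenance hemodialysis will normally have a session within days of randomization. Once that session is recorded, the patient has the outcome, and the allocated treatment had no part in it. Such events add about the same number to each arm and so shrink the ratio between arms. If new renal replacement is uncommon, a handful of these patients can make up a large share of all events, and an uneven split of them can resemble a treatment effect.

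The protocol deals with the same problem elsewhere. Patients already in the ICU or ventilated at screening are excluded, and long-standing night-time airway support is set aside: "The use of BIPAP or CPAP at night or when sleeping for sleep apnea is not considered non-invasive mechanical ventilation or organ support". Chronic hemodialysis has no matching provision. A reader of the reported odds ratio will probably take it to describe new renal failure.

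**Working it through.** **The plan's own figures.** The documents give no renal replacement rate, no dialysis prevalence and no power for this outcome, so there is nothing specific to reproduce. The arm size used below is the 231 per group of Protocol 7.1. That figure is consistent with its inputs (50% versus 35%, 90% power, two-sided): a fixed-design calculation gives 227 per group at alpha 0.05 and 229 at the SAP's final level of 0.048. It does not depend on this point.

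**Model.** Let q be the share of each arm on maintenance hemodialysis at entry with a session recorded afterwards, and p the risk of new renal replacement in the others.

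- Observed risk: r = q + (1 − q)p
- Observed odds ratio: [r_E/(1 − r_E)] / [r_C/(1 − r_C)]
- Observed risk difference: r_E − r_C = (1 − q)(p_E − p_C)
- Share of control events that are pre-existing: q / r_C

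Both q and p are assumptions. I take q = 1%, 2% and 3% (about 2.3, 4.6 and 6.9 patients per arm of 231) and a halving of risk from control rates of 2% to 10%.

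**One case in full** (3% versus 1.5%, q = 2%):

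- Control: 0.02 + 0.98 × 0.03 = 0.0494
- Experimental: 0.02 + 0.98 × 0.015 = 0.0347
- Odds ratio: (0.0347/0.9653) / (0.0494/0.9506) = 0.69, against a true (0.015/0.985) / (0.03/0.97) = 0.49
- Pre-existing share of control events: 0.02/0.0494 = 40%

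**All cases**

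| New events, control vs experimental | True OR | OR at q = 1% / 2% / 3% | Pre-existing share of control events | Risk difference in points, q = 0 to q = 3% |
|---|---|---|---|---|
| 2% vs 1% | 0.50 | 0.66 / 0.74 / 0.80 | 34% / 51% / 61% | −1.00 to −0.97 |
| 3% vs 1.5% | 0.49 | 0.62 / 0.69 / 0.74 | 25% / 40% / 51% | −1.50 to −1.46 |
| 6% vs 3% | 0.485 | 0.55 / 0.61 / 0.65 | 14% / 25% / 34% | −3.00 to −2.91 |
| 10% vs 5% | 0.47 | 0.52 / 0.55 / 0.59 | 9% / 17% / 24% | −5.00 to −4.85 |

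**Power at 231 per arm.** For 6% versus 3%, power falls from 34% (q = 0) to 29%, 25% and 22%. For 10% versus 5%, it falls from 53% to 48%, 44% and 40%. For 3% versus 1.5%, it is about 19% with new events only and 10% to 15% as written.

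**Chance imbalance.** If ten such patients are randomized, the probability that they split 7–3 or worse is 2 × (120 + 45 + 10 + 1)/1024 = 0.34.

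**The case against.** Several stronger readings are tempting, and the documents do not support them.

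- *Every dialysis patient becomes an event.* No. The definition names only CRRT and intermittent hemodialysis, so peritoneal dialysis alone is not counted. Outcomes come from hospital records, and SAP 4.6 treats secondary outcomes as in-hospital measurements. The telephone contact in Protocol 6.3 is specified for vital status, and for ventilation status in patients discharged ventilated. Outpatient sessions after discharge may never be recorded.
- *Dialysis patients were meant to be enrolled.* The rows for clearance below 30 also cover acute kidney injury and chronic disease without dialysis. All that can be said is that dialysis patients are not excluded.
- *The comparison is biased toward one arm, or is invalid.* Randomization balances these patients in expectation. The comparison of the proportion receiving renal replacement, which is what the plan literally states, remains valid. Chance imbalance is reflected in the confidence interval.

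The defence can also say that the practical loss is small. The outcome is one of 15 that Protocol 7.2 calls exploratory. It is not part of the primary composite or of organ support in Appendix 4. Power is low under either definition, and the risk difference barely moves.

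All of this stands, and it limits the severity. It does not remove the defect: SAP 4.3 reports an odds ratio, which is the measure that constant background events distort, and no other section corrects for it.

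**Conclusion.** The point holds as a minor one. The text of both documents establishes that maintenance-hemodialysis patients can be randomized and that a recorded session after randomization counts as an event in either arm. The direction of the effect, attenuation of the odds ratio, follows from the definition whenever the treatment has any effect and at least one such patient is enrolled.

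The size rests entirely on assumed rates. With 1% to 3% of patients on hemodialysis at entry, a halved risk would appear as an odds ratio between 0.52 and 0.80, with the worst dilution where new events are rarest. If no such patients are enrolled, nothing changes. The primary analysis, the sample size and the interim rules are not involved.

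**What to change.** In SAP 2.2.1 item 7 and protocol secondary outcome 7, define the outcome as renal replacement newly started after randomization. Analyse it in participants who were not receiving maintenance dialysis, CRRT or intermittent hemodialysis at randomization, and show the as-written count for all randomized patients as a supplementary line. Because the restriction uses pre-randomization status only, the randomized comparison is preserved.

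Baseline dialysis status should come from the medical history or the eCRF if it is recorded there. The eCRF is not among the documents, and Table 5 describes the medical history item without naming dialysis, so the sponsor needs to confirm this. Otherwise the hospital records already used for outcomes can supply it, under one rule for both arms. The Day 1 renal replacement entry in Table 5 is not sufficient alone: it misses patients whose session falls on another day, and as described it does not separate sessions before randomization from those after.

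The cost is a slightly smaller denominator for this one outcome and possibly a small chart look-up. Eligibility, treatment and the primary analysis do not change.
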